5.6 Monitoring of transfusion need. All the transfusions carried out in all the patients before the 36th week of PMA will be recorded. Before and after every transfusion, HbF, HbA and capillary arterial-blood gas will also be tested. Blood samples for CBC and/or reticulocytes will only be taken if clinically necessary and not for study-related reasons.

5.7 Monitoring of HbF and HbA levels. Three capillary blood samples will be taken every week for dosing HbF and HbA. If other tests for routine assistance, or for blood units cross-match, are carried out, part of the blood sample will be recovered for dosing HbF and HbA. The dosage will be carried out on samples that were stored at the Hematology Service of the Foundation, through HPLC on lysate samples. This procedure needs very low sample volumes (50-100 µL).

5.8 Definition of the prematurity-related pathologies (ROP, BPD, NEC and IVH). ROP (grade I-IV) will be diagnosed based on the criteria of the “International Committee for the Classification of Retinopathy of Prematurity” [49]; NEC will be diagnosed based on the criteria of Bell [50]; BPD is diagnosed when an infant continues to need additional oxygen after 28 days of age, at the 36th week of PMA [51]; the diagnosis of IVH will be based on the criteria of Papile [52].

5.9 Recording of clinical data and laboratory parameters. For each patient, the following parameters will be recorded on specific case report forms: GA and birth weight, sex, ethnicity, twin birth, PMA, respiratory support, additional oxygen, length of the hospitalization in the NICU, number of days under antibiotic therapy and PMA when leaving the hospital. All the causes of mortality and morbidity occurred within the 36th week of PMA will be recorded (infectious episodes, hemorrhagic events, kidney failure, thromboembolism, surgical complications, etc.). All the possible adverse events occurred within that date would also be recorded (for example, the unexpected adverse events, including all the alterations of the laboratory parameters, regardless of their seriousness). All the hematological (Hb, HbF% and HbA%, Hct) and transfusion data (date, number of transfusions, type of transfusion, volumes of transfused RBC) will also be recorded. For all those patients who were discharged before the completion of the 36th week of PMA, the clinical evaluation, the determination of HbF on capillary blood and the collection of data will be carried out at ambulatory level.

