10. STUDY-RELATED RISKS AND BENEFITS

Due to the type of the patients, the volume of blood necessary to carry out the expected tests is a critical element. For this reason, the study was designed not to entail any more blood samples than those already taken to assist the patient. The HbF will be determined by using the capillary blood residue of other routine tests. As for the UCB-RBC transfusion, the immune

and infection risks are lower than A-RBC transfusions. Screening tests, adult and cord red cells production and storage techniques are comparable; the units of cord blood, unlike those of adult blood, are only released after checking the negativity of the microbial cultures. This procedure is due to the methods of cord blood collection and, if it guarantees sterility on the one hand, on the other, it prevents it from being transfused before five days have passed (i.e. the days necessary to detect any microbial contamination). This means that fetal blood transfusions could be less fresh than adult blood transfusions, even though a recent randomized study has not proven any remarkable differences in the safety and efficacy of the transfusions that were conserved for \pm 7 days [25]. Among the expected benefits of UCB-RBC transfusions is a lower risk of developing prematurity-related pathologies and the certainty that donors are CMV-negative.

This study could have a strong impact on the National Italian Health Service. In fact, it is only the first of many studies to test if the prevalence and seriousness of the prematurity-related pathologies can be reduced by applying an innovative transfusion approach, the aim of which is that of maintaining HbF at physiological levels during various weeks after birth. As far as we know, this approach has never been studied. It is also important to underline that the strategy of transfusing cord blood also has an economic impact since it is based on unused existing economic resources. Nowadays, Italian public Cord Blood Banks collect a very high number of CB units that cannot be used for transplants: in 2016, 14,661 CB units were collected but only 983 (6.7%) of them were listed for transplants.

The results of this study could be the assumption of many other randomized studies that aim to determine the negative impact of blood components on preterm infants and especially to establish if it can be a consequence of HbF reduction.

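### Sections 5.7 and 5.9 can require HbF blood draws that section 10 says the study does not make

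*Combined protocol and SAP*

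**What the plan says.** Section 10 makes two statements without exception. The first is that "the study was designed not to entail any more blood samples than those already taken to assist the patient". The second is: "The HbF will be determined by using the capillary blood residue of other routine tests". It gives the reason as well: the blood volume that the tests need is critical in these infants.

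The procedures are worded differently.

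- **5.7** opens with "Three capillary blood samples will be taken every week for dosing HbF and HbA". It then says "If other tests for routine assistance, or for blood units cross-match, are carried out, part of the blood sample will be recovered" for the same assays. It adds that "This procedure needs very low sample volumes", given as 50-100 µL.
- **5.9** says that, for infants discharged before completing 36 weeks PMA, "the determination of HbF on capillary blood and the collection of data will be carried out at ambulatory level".
- **5.6** says "Before and after every transfusion, HbF, HbA and capillary arterial-blood gas will also be tested", and follows this with "Blood samples for CBC and/or reticulocytes will only be taken if clinically necessary and not for study-related reasons".

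**The concern.** The no-extra-samples statement in section 10 is the protocol's answer to a risk that it raises itself. Section 1 lists repeated sampling among the factors that worsen anaemia of prematurity, and the trial enrols infants born at 30 weeks or earlier and/or weighing 1000 g or less. A risk statement of that kind should be something that the procedures deliver.

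Staff work from section 5. If a scheduled HbF value has no routine sample behind it, 5.7 read alone tells them to take one, and section 10 says that this does not happen. For an infant already at home, 5.9 asks for capillary blood when the protocol names no routine test that would provide it. The stake is whether the safeguard described in section 10 actually governs what is done to the infant.

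**Working it through.** The protocol gives no figure to reproduce on this point. The check sets each procedure against section 10 and asks two questions: is the blood limited to residue, and what happens when there is no residue?

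1. **5.7, first sentence.** It sets a fixed frequency and gives HbF/HbA measurement as the purpose of the sample. It contains no limit to residual blood.
2. **5.7, second sentence.** Recovery of leftover blood is conditional on other tests being done. The sentence covers the case where routine blood exists. It does not say that a scheduled sample is dropped when none exists.
3. **5.9.** It requires HbF on capillary blood at outpatient level. It names no routine outpatient blood test and states neither the number of visits nor the number of samples.
4. **5.6.** It requires HbF and HbA to be tested around each transfusion, alongside a capillary blood gas. It does not say that a separate sample is drawn, and 5.7 names cross-match blood as a source. Residue is therefore plausible here. The sentence against study-related sampling covers only CBC and reticulocytes, but that silence on HbF does not create a draw.
5. **Section 10.** It limits HbF to residue without exception. Neither 5.7 nor 5.9 refers to it.

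**Frequency in hospital.** Let r be the number of the three weekly samples under 5.7 that routine blood can supply, with r between 0 and 3. Study-only draws per week = 3 − r.

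- If routine care covers all three: 3 − 3 = 0.
- If routine care covers none: 3 − 0 = 3.

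The protocol does not give the frequency of routine sampling, so the range cannot be narrowed.

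**Frequency after discharge.** It cannot be calculated, because 5.9 states no number of samples.

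**The case against.** The strongest reply is that section 10 already settles the matter. Its limit applies to the whole study and names HbF. A general rule need not be repeated in each procedure to bind it. Read together, the first sentence of 5.7 gives the frequency, the second gives the source, and section 10 rules out any other source. This may well be the intent, and it means that the text can be reconciled. It does not remove the problem. 5.7 describes samples taken for the assay and makes recovery conditional, and neither 5.7 nor 5.9 says to skip a value when no residue exists. The reply is weakest for 5.9, where no routine test is specified at all.

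A second reply is that no harm is shown. That is correct. Section 1 describes repeated laboratory sampling in preterm infants, so routine blood in hospital may always be enough.

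A reader might go further than the text allows in three ways:

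- **That infants will undergo three extra capillary draws a week.** This is only the upper end of a range that starts at zero.
- **That the assay volume measures the blood lost to the study.** The 50-100 µL is what one assay needs. Some or all of it may be residue, and a dedicated draw may take a different volume.
- **That 5.6 also imposes study-only draws.** It asks only for a test, and the cross-match and blood-gas samples are natural sources.

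**Conclusion.** The point holds as an inconsistency between a safety statement and the procedures meant to honour it. As written, 5.7 and 5.9 can require study-only draws that section 10 says do not occur. The size is 0 to 3 draws a week in hospital, possibly nil, and an unstated number after discharge, where the gap is clearest.

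Confidence is high on the wording. No consequence is established: the documents show no effect on outcomes, power or any result. A reader might also infer that parents were misinformed. That is not supported, because the consent annex is not available for review.

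The conclusion rests on one assumption, that staff apply section 5 as written and do not read section 10 into it. The correction should be made because it is cheap and concerns a risk that the protocol itself calls critical.

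**What to change.** **In 5.7 and 5.9**, state that HbF/HbA is measured on residual blood from routine tests, blood gases or cross-match, up to three times a week, and that a scheduled weekly value is skipped when no residue exists.

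**In 5.6**, state that the pre- and post-transfusion HbF uses the cross-match or blood-gas sample. This keeps the first endpoint listed in 3.5 without a separate draw.

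**Optional exception.** The sponsor may want to guarantee the 32-week primary value or the last-control/ambulatory value. If so, allow a dedicated capillary draw for those only, and correct section 10 to disclose the exception and its maximum number. One draw at each of the two time points would be 1 + 1 = 2 per infant. The sponsor has to set the number, because 5.9 does not give one. Without the exception, section 10 can stand as it is.

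**Cost.** The change is wording in 5.6, 5.7 and 5.9, and in section 10 if the exception is used. It needs no extra patients. Some non-primary weekly HbF values may be missing. How many cannot be estimated without the routine sampling frequency. Skipped values should be recorded as such, because the weekly values would presumably feed the inpatient HbF average in the secondary outcomes. If the exception is not adopted, the 32-week and last-control values also depend on residue being available.

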6. STATISTICAL CONSIDERATIONS

6.1 Definition of analysis sets

- **Enrolled (E) set or Intent-to-treat (ITT) analysis.** It will comprise all the enrolled patients, regardless of the administration or not of RBC transfusions.
- **Treated (T) set.** This group will comprise all the patients who were at least administered one transfusion, regardless of the completion of the observation period (36th week of PMA). Excluded from this set are the enrolled patients who were not transfused.
- **Per-Protocol (PP) set.** This group will comprise all the transfused patients who completed the observation period (36th week of PMA) or who died after completing it.

6.2 Calculation of sample size. The main goal of the study is to correlate the average HbF levels to the type of transfusion (UCB-RBC or A-RBC). With a population of 25 patients that will be studied during the following 8 weeks and a mortality rate of 1.9 patients/month, we expect to have 196 weekly doses of HbF to correlate to 98 transfusions. The total expected number of transfusion from birth to the completion of the 36th week of PMA was calculated to be around four transfusions per patient, with an UCB-RBC:A-RBC ratio of 1:1. In fact, for those patients with birth-determined characteristics similar to those of the studied population, the average number of transfusions within the 36th week of PMA is around 4 transfusions/patient [25], while in our previous study the average number of transfusions was 3 ± 1.7 [46]. In accordance with the literary data, preterm infants have an expected HbF concentration between 85% and 90% at birth and between 70% and 75% at the 36th week of PMA [54]. We expect that for the newborns who will not be transfused the HbF levels will stay in this range (70%-90%), while for the patients who will be transfused with adult red cells, HbA will dilute HbF. Even though there are no literary data yet, if we know the volume of transfused red cells (20 ml/kg) and the patient's blood volume, we can also assume that, for every adult red cell transfusion, HbF will be reduced by 15-20% compared to the pre-transfusion values until reaching levels lower than 20% among those patients who were transfused more than 4 times with adult blood.

6.3 Statistical data analysis. The continuous variables will be expressed as mean (\pm SD) or as median (interquartile ranges, IQR); all deviations from normality will be detected with the Shapiro-Wilk test. The categorical variables will be expressed as n, (%), percentage). HbF levels in different type of transfusions will be compared in univariate analysis Mann-Whitney U test, end Kruskall Wallis test). Similarly, the transfusion efficacy analysis will be carried out based on a UCB-RBC and A-RBC non-inferiority study design by comparing the average time interval between two subsequent transfusions and the average post-transfusion capillary Ht

increase (Δ Ht) (Mann-Whitney U Test). The transfusion sample included in the study makes it possible to detect a difference between groups that is equal to at least 1 standard deviation with type I error $\alpha = 0.05$ and type II error $\beta = 0.2$ and a medium effect size (0.6). The correlation between the type of transfusion and other variables (prematurity related pathologies) will be tested using Fisher's exact test. Secondarily, in order to evaluate the effect of HbF reduction on the onset of prematurity-related pathologies, the levels of HbF levels will be inserted in a multiple linear regression model, by expressing the correlation between the onset of prematurity-related pathologies and the variables in terms of odds ratios (ORs \pm 90% confidence interval).

6.4 The primary outcome analysis will be tested on "E", "T" and "PP" sets. Transfusion efficacy outcome will be tested on "T" and "PP" sets.

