2. OBJECTIVES OF THE STUDY

The objective of the study is to investigate the correlation between the levels of HbF and the use of umbilical cord blood red cell concentrate transfusions in ELBW preterm infants and/or infants who were born before the 30th week of gestational age (GA). Since transfusions are one of the main mechanisms to reduce HbF, they will be carried out with umbilical cord blood red cell concentrates (UCB-RBC). Our objective is to demonstrate that UCB-RBC transfusions, until the 32nd week of PMA, guarantee average levels of HbF that are higher than in adult-RBC (A-RBC) transfusions. The following outcomes were defined:

Primary outcome:

- Average levels of HbF at 32nd week of PMA in patients receiving different transfusion support.

Secondary outcomes:

- To show that UCB-RBC transfusions are not less effective than A-RBC transfusions, as for the post-transfusion increase in the hematocrit and the interval between two transfusions.
- To show the association between average levels of HbF during the inpatient stay and comorbidities (ROP, BPD, NEC, PVL and IVH) or deaths occurred within 36 weeks of PMA.

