3. EXPERIMENTAL DESIGN

3.1 Study design. This study is a prospective non-randomized study to evaluate the correlation between the reduction in the level of HbF (based on the relation between HbF and HbA) before the 36th week of PMA and the type of transfusion (UCB-RBC or A-RBC).

3.2 Duration of the study. The study will have an overall duration of one year. The enrollment of patients will last 10 months. Considering the volume of activity of our NICU and the type of eligible patients, such a period of time was considered adequate to enroll the number of patients necessary to reach the established objectives. As for the transfusions (UCB-RBC or A-RBC), the intervention phase will last from the enrollment to the completion of the 32nd week of PMA, while the weekly monitoring of HbF will continue until the completion of the 36th week of PMA.

3.3 Early study termination. The study will be terminated with the occurrence of adverse events that can be risky for the patients or if the Proposer thinks it is necessary, based on the evaluation of safety data.

3.4 Study termination. The study will be considered over when the collected data make it possible to draw up the final report.

3.5 Study endpoints.

- HbF levels before and after each transfusion;
- Average HbF levels (at 32 weeks of PMA; at last control)
- Prevalence of ROP and/or BPD and/or NEC and whatever health problems (infectious pathologies, hemorrhages including IVH, kidney failure, thromboembolism, surgical complications, etc.) before the 36th week of PMA;
- Transfusion efficacy of UCB-RBC compared to A-RBC (all transfusions before the 36th week of PMA, evaluated based on a) average time interval between two subsequent transfusions and b) average increase in the post-transfusion capillary hematocrit (Δ Hct).

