4.1 Eligibility criteria

4.1.1 Inclusion criteria. All the patients who will be included in the study will have to meet the following inclusion criteria:

- Birth gestational age \leq 30 weeks and/or birth weight \leq 1000 grams;
- Need of transfusions before the 32nd week of PMA, according to the guidelines currently used by the NICU.

4.1.2 Exclusion criteria. None of the enrolled patients can be affected by one or more than one of the following pathologies:

- mother-fetus isoimmunization;
- hydrops fetalis;
- chromosomal anomalies and congenital malformations;
- acute hemorrhage at birth.

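### The primary HbF is taken at 32 weeks PMA, but the analysis sets and product classes used for it have no 32-week cut-off, so later events can decide who is compared with whom

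*Combined protocol and SAP*

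**What the plan says.** **Provisions that point to 32 weeks.** Section 2 gives the primary outcome as "Average levels of HbF at 32nd week of PMA in patients receiving different transfusion support" and words the aim as "Our objective is to demonstrate that UCB-RBC transfusions, until the 32nd week of PMA, guarantee average levels of HbF" above those seen with adult blood. Under section 3.2, "the intervention phase will last from the enrollment to the completion of the 32nd week of PMA". Inclusion criterion 4.1.1 requires "Need of transfusions before the 32nd week of PMA". Sections 5.2 and 5.5 have the 32-week date listed for each infant and checked at each blood request.

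**Provisions that point to 36 weeks.** Section 3.1 relates product type to the fall in HbF before week 36. Section 3.2 adds that "the weekly monitoring of HbF will continue until the completion of the 36th week of PMA". Section 5.6 states: "All the transfusions carried out in all the patients before the 36th week of PMA will be recorded". The planning count in section 6.2 is "The total expected number of transfusion from birth to the completion of the 36th week of PMA".

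**Analysis rules.** Section 6.1 defines the Treated (T) set: "This group will comprise all the patients who were at least administered one transfusion, regardless of the completion of the observation period". The Per-Protocol (PP) set takes transfused infants who completed observation to week 36, including those who died after that. Section 6.3 compares HbF between types of transfusion by Mann-Whitney and Kruskal-Wallis tests. It does not say how an infant who received both products is classed, or up to what date transfusions count. Section 6.4 applies the primary analysis to the Enrolled (E), T and PP sets.

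**The concern.** A transfusion at week 34 cannot change an HbF value measured at week 32. If it can still move an infant from one product group to another, or into or out of an analysis set, the primary comparison is conditioned on something that happened after its outcome.

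Three routes are open:

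1. **Product class.** An infant given UCB-RBC only up to the 32-week sample and A-RBC afterwards may be classed as A-RBC or mixed. This can happen even when criterion 4.1.1 is strictly applied.
2. **T membership.** An infant first transfused after week 32 meets the T definition, although the 32-week value was untransfused.
3. **PP membership.** An infant with a valid 32-week HbF who dies or leaves between weeks 32 and 36 is removed.

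The study is non-randomised, has 25 infants, and assigns product by availability, so many infants will receive both products. The single-product groups are small, and losing one or two infants for a post-outcome reason matters. A rule left unwritten can also be chosen after the HbF values are known.

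**Working it through.** **Inputs from the plan (6.2).** 25 infants; about 4 transfusions each to week 36 (3 ± 1.7 in the earlier single-centre study); UCB-RBC to A-RBC ratio 1:1.

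**The plan's own count.** 25 × 4 × (1 − 0.019) = 98.1, and 25 × 8 × (1 − 0.019) = 196.2. These match the stated 98 transfusions and 196 HbF measurements if 1.9 is read as a percentage (the plan prints it as patients per month). So 4 per infant to week 36 is the figure behind the plan.

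**Input not in the plan.** The share *f* of transfusions given by 32 weeks. Section 1 says only that it is most of them. Assumed range: 95% to 70%.

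**Model (assumed).** Transfusion counts are Poisson with mean 4, and each unit is independently UCB-RBC or A-RBC with probability ½. Each product then has mean 2*f* before week 32 and 2(1 − *f*) after.

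**Route 1: UCB-RBC only by 32 weeks, A-RBC later.**

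- UCB-only at 32 weeks: 25 × (1 − e^(−2f)) × e^(−2f)
- Probability of a later A-RBC unit: 1 − e^(−2(1−f))

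| *f* | UCB-only at 32 weeks | P(later A-RBC) | Infants who could be moved |
|---|---|---|---|
| 95% | 3.2 | 0.10 | 0.3 |
| 90% | 3.4 | 0.18 | 0.6 |
| 80% | 4.0 | 0.33 | 1.3 |
| 70% | 4.6 | 0.45 | 2.1 |

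For example, at *f* = 80%: e^(−1.6) = 0.202; 25 × 0.798 × 0.202 = 4.03; 1 − e^(−0.4) = 0.330; 4.03 × 0.330 = 1.3.

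With a mean of 3, the ends of the range are again 0.3 and 2.1. If every later unit were adult blood (an assumption; the plan does not say so), the probability becomes 1 − e^(−4(1−f)). At *f* = 80% that is 0.55, giving 4.03 × 0.55 = 2.2 infants.

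**Route 2: in T only through a later transfusion.** 25 × e^(−4f) × (1 − e^(−4(1−f))) gives 0.1 (95%), 0.2 (90%), 0.6 (80%) and 1.1 (70%) of 25, ignoring criterion 4.1.1. If that criterion is applied, the number is near zero.

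**Route 3: PP.** The plan gives no loss figure for weeks 32 to 36. Four weeks is 4 / 4.345 = 0.92 month. Taking all 25 as alive at 32 weeks and the plan's mortality as constant, deaths in that window would be 25 × 0.019 × 0.92 = 0.4 (1.9 as a monthly percentage) or 1.9 × 0.92 = 1.7 (1.9 patients per month as printed). Withdrawals would add to this.

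**Direction under route 1.** The plan expects adult blood to dilute HbF, so a moved infant has a 32-week HbF free of that dilution.

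- Counted as A-RBC: the adult-blood group's HbF rises and the difference shrinks.
- Counted as mixed: the A-RBC-only group is unaffected and the mixed group's HbF rises.

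Under either rule the UCB-only group keeps only infants who received no later adult blood.

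**The case against.** The strongest reply is that the plan already intends a 32-week limit. The objective, the intervention phase and the date check in 5.5 all say 32 weeks. The 36-week provisions serve other endpoints: HbF at last control, morbidity before week 36, and transfusion efficacy over all transfusions to week 36. The 98 transfusions in 6.2 are paired with weekly HbF measurements, not with one 32-week value per infant.

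Much of this stands. A reader might infer that infants are classed by products given after the outcome. No section says so; 6.3 has no classing rule. A reader might also take the T definition as setting a 36-week exposure window. It does not: the week-36 reference there describes the observation period, and the transfusion has no date attached. Nor do the documents support a firm claim of bias towards no difference. That needs late-switching infants to be counted as A-RBC, and the Kruskal-Wallis test in 6.3 leaves room for a separate mixed group. The T-set route is minor given criterion 4.1.1. Counting every infant with any transfusion after week 32 would overstate the problem, because infants already mixed by then cannot change class.

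What the reply does not answer is that 6.4 applies the primary analysis to sets whose written definitions ignore the 32-week date. For PP this is an explicit rule, not a gap. Section 3.1 also frames the main correlation to week 36, so the 32-week intention is not uniform.

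**Conclusion.** The point holds as a mismatch between the outcome date and the analysis rules. The plan permits post-outcome transfusions to determine product class, and its PP definition makes survival and follow-up to week 36 a condition for analysing a 32-week value.

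The expected number is small, but so is the affected group: about 0.3 to 2.1 of 25 infants, or roughly 10% to 45% of a UCB-only group of 3 to 5. This rests on Poisson counts, independent 1:1 product choice and an assumed 95% to 70% of transfusions by 32 weeks. Because product depends on blood-group availability, units may cluster by type within an infant. The UCB-only group would then be larger and switching rarer. The direction of bias is undetermined until the classing rule is written. It should be corrected before the HbF data are examined.

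**What to change.** In 6.1, 6.3 and 6.4, for the primary outcome only:

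- State which HbF sample is the 32-week value. Section 5.7 foresees three samples a week, so the cut-off needs a named sample.
- Class each infant as UCB-RBC only, A-RBC only or mixed, using only transfusions given before that sample, and state how the mixed group enters the comparison.
- Define T and PP as infants with at least one transfusion before that sample. An infant with none stays in E as untransfused.
- Remove completion of week 36 as a condition for PP.
- Keep transfusions from 32 to 36 weeks for the secondary outcomes.

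Section 5.2 labels the 32-week date as the end of the A-RBC intervention phase, while 3.2 applies it to both products. The two passages must be reconciled, because the classing rule relies on that date.

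The cost is wording. Transfusion dates and types are already collected (5.9). An occasional infant may leave the primary T set.

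### The Per-Protocol set requires follow-up to 36 weeks PMA although the primary outcome is HbF at 32 weeks, so one of the three primary analyses selects on events after the measurement

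*Combined protocol and SAP*

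**What the plan says.** All references are to the combined protocol and SAP.

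- **Primary outcome (section 2):** "Average levels of HbF at 32nd week of PMA in patients receiving different transfusion support".
- **End of treatment (section 3.2):** "the intervention phase will last from the enrollment to the completion of the 32nd week of PMA".
- **End of follow-up (section 3.2):** "the weekly monitoring of HbF will continue until the completion of the 36th week of PMA", four weeks after the primary time point.
- **PP set (section 6.1):** transfused infants who "completed the observation period (36th week of PMA) or who died after completing it".
- **T set (section 6.1):** infants with at least one transfusion, "regardless of the completion of the observation period (36th week of PMA"). The E set takes everyone enrolled.
- **Use of the sets (section 6.4):** the primary outcome is tested on E, T and PP. For efficacy, "Transfusion efficacy outcome will be tested on" T and PP. No set is called the main one.
- **Death (section 2):** a secondary objective relates average HbF to comorbidities or death up to 36 weeks PMA.

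**The concern.** Membership of an analysis set for a 32-week outcome should be settled by 32 weeks. Here it depends on what happens in the next four weeks. An infant who was transfused, reached 32 weeks and has the primary measurement is excluded from PP if death or loss to follow-up comes before 36 weeks.

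That exclusion may be informative. The introduction cites transfusion as a risk factor for survival, and section 2 treats death by 36 weeks as something HbF may be associated with. A PP comparison of HbF is then restricted to infants selected on a later event that the plan itself thinks may be related to both exposure and outcome.

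The definition also contains nothing about adherence, such as whether HbF was measured as planned or whether a major deviation occurred. It is in effect a completers set under a per-protocol label. Because no set is decisive, the plan does not say what follows if PP disagrees with E or T.

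**Working it through.** **1. Who is in which set.** Take a transfused infant with HbF measured at 32 weeks PMA:

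| Later course | E | T | PP |
|---|---|---|---|
| Completes 36 weeks | in | in | in |
| Dies after completing 36 weeks | in | in | in (already a completer) |
| Dies between 32 and 36 weeks | in | in | out |
| Lost alive between 32 and 36 weeks | in | in | out |

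The second row shows that the clause on death after completion adds nobody. If death before completion was meant, the third row would change to in and only the fourth would remain. The documents do not settle this.

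**2. The plan's own figures.** Section 6.2 gives 25 infants, 8 weeks, a mortality of 1.9 patients/month, about four transfusions each, and expects 196 weekly HbF values and 98 transfusions. Without losses these would be 25 × 8 = 200 and 25 × 4 = 100.

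- *A single 1.9% loss:* 25 × 0.981 × 8 = 196.2 and 25 × 0.981 × 4 = 98.1. Both figures reproduce.
- *1.9% per month, even attrition:* the weekly loss is 0.019 × 25 ÷ (52/12) = 0.110 infants. With mid-week times 0.5 to 7.5, which sum to 32, infant-weeks are 200 − 0.110 × 32 = 196.5. At 4/8 transfusions per infant-week this gives 98.2. Both are close to the stated figures.
- *1.9 deaths per month, even attrition:* the weekly loss is 1.9 ÷ (52/12) = 0.438. Infant-weeks are 200 − 0.438 × 32 = 186.0, and transfusions 93.0. Neither figure reproduces.

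The percentage reading fits the plan's figures. The words as printed do not.

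**3. Deaths between 32 and 36 weeks.** Both calculations assume a constant rate with all 25 infants followed together. The documents give no rate for this window.

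- 1.9% per month: 0.110 × 4 = 0.44 infants.
- 1.9 deaths per month: 0.438 × 4 = 1.75 infants, or 1.75 ÷ 25 = 7%. About 25 − 1.75 = 23.25 would be alive after four weeks and 21.5 after eight.

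At four transfusions per infant, PP would omit at most about 0.44 × 4 ≈ 2 or 1.75 × 4 = 7 transfusions from the efficacy analysis. Infants lost alive are extra, and no rate is given for them.

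**4. Effect on precision, larger reading.** Assume infants split 1:1, a 1 SD difference, two-sided α = 0.05 and Mann-Whitney efficiency 0.955. Power is Φ(√(n/2) − 1.96), with n = 0.955 × N/2 per group.

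- N = 23.25: n = 11.10, power 0.65.
- N = 21.5: n = 10.26, power 0.62.

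The loss of precision is small. The issue is selection.

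**The case against.** The strongest reply is that nothing is lost from the study. T has no completion requirement, and section 6.4 uses it for both the primary outcome and efficacy. Every infant whom PP omits is analysed in E and T, and every transfusion in T. Comparing T with PP would itself show what the exclusion does. This stands, and it limits the point to a subset of the planned analyses.

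A 36-week rule also suits other endpoints. Section 3.5 counts transfusions and morbidity up to 36 weeks and lists "Average HbF levels (at 32 weeks of PMA; at last control"), and section 5.8 assesses BPD at 36 weeks. A completers set is coherent for those. However, section 6.4 assigns PP only to the primary outcome and transfusion efficacy, so this does not justify the rule for a 32-week measurement.

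The adherence complaint is partly about a label. Section 5.5 allows either product depending on availability, so a criterion based on product choice would separate few infants.

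Three stronger readings are tempting, and the documents support none of them:

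- *Valid primary values drop out of the primary analysis altogether.* They drop out of PP only.
- *As many as 3.5 infants are removed.* That is the whole 8-week total on the literal reading (0.438 × 8), and it needs every death to fall after 32 weeks, contrary to a constant rate.
- *The PP result is biased in a known direction.* Nothing in the plan shows whether excluded infants would have higher or lower HbF within each product group.

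**Conclusion.** The point holds in a limited form. As written, PP conditions a 32-week outcome on survival and follow-up to 36 weeks. The mismatch follows from the definitions and needs no estimate.

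Its size is modest and uncertain: about 0.4 infants removed by death if 1.9 is a monthly percentage, about 1.75 of 25 if it is deaths per month, plus an unknown number lost alive. Both figures rest on a constant rate and a single cohort of 25, whereas enrolment actually runs over 10 months. The possibility of selection is established, but its direction is not.

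It affects one of three primary analyses and one of two efficacy analyses. It carries weight mainly because no set is named as decisive, so a conclusion could rest on PP. The clause on death after completion needs clarifying on any reading.

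**What to change.** - **PP for the primary outcome (section 6.1):** infants transfused before completing 32 weeks PMA, with HbF measured at 32 weeks and no major protocol deviation (to be listed). No survival or follow-up requirement after 32 weeks.
- **36-week completion:** keep it only for outcomes assessed to 36 weeks, or as a descriptive status.
- **The clause on death after completion:** delete it, or correct it if something else was meant.
- **Main set (section 6.4):** name one for each outcome and call the others supportive. T is the natural choice for transfusion efficacy because it already includes all transfusions.
- **Section 6.2:** state whether 1.9 is a percentage or a count, so that the expected loss can be calculated.

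The cost is a few sentences in sections 6.1, 6.2 and 6.4. No further infants, samples or data are needed.
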